### 10.2 Reporting of adverse events

Complete and appropriate data on all AEs experienced during the clinical trial will be reported in the AE pages of the CRF on an ongoing basis for the duration of the reporting period.

It is important that each AE report includes a description of the event, its seriousness status and criteria, duration, severity, relationship to the investigational medicinal product, other causality factors (if any), any concomitant medications dispensed, concomitant procedures prescribed or other actions taken and its outcome at the end of the reporting period.

### 10.3 Serious Adverse Events

A Serious Adverse Event (SAE) is defined as one of the following:

- An event that causes the death of the patient.
- A life-threatening\* event.
- An event causing hospitalisation\*\* or prolongation of existing hospitalisation.
- An event causing persistent or significant disability or incapacity.\*\*\*
- An event causing a congenital anomaly or birth defect in the offspring of a subject treated before or during pregnancy.
- Important medical events (i.e., not immediately life-threatening or do not result in death or hospitalisation but require urgent and intensive intervention to prevent one of the outcomes listed in the definition above, for example, intensive treatment at home or in an emergency room for bronchospasm or convulsion)

\* The term 'life-threatening' refers to an event in which the patient was at risk of death at the time of event; it does not refer to an event that hypothetically might have caused death if it were more severe.

\*\* A hospitalisation is defined as an overnight stay, including time spent in an emergency room, for an AE (although subject has to have been admitted to a ward or remained in hospital >24 hours). A prolongation of existing hospitalisation is defined as an additional overnight stay. Elective surgery is not classified as an SAE. For the purposes of this trial, admission for an elective surgical procedure/ routine procedure/ routine assessment will not be considered an SAE unless there is a prolongation to the anticipated duration of hospitalisation for a procedure/assessment of that nature. Any other unanticipated outcome of a procedure/assessment that meets the definition of a serious adverse event should be reported.

\*\*\* The term 'persistent or significant disability or incapacity' refers to an event that results in a substantial or permanent disruption of patient's ability to carry out normal life functions.

Pregnancy is not considered to be an adverse event. However if any female becomes pregnant during the course of the trial, she will be followed up to determine the outcome of both the mother and foetus. Also if the partner of a male patient enrolled in the trial becomes pregnant, the mother and foetus will also be followed-up to determine the outcome of both.

### 10.4 Reporting Serious Adverse Events

All SAEs occurring during the trial or within 7 days following the completion of the trial by the patient must be reported to The Sponsor by fax or email within 24 hours of the investigator becoming aware of the SAE.

SAE EMERGENCY CONTACT DETAILS	
[REDACTED]	[REDACTED]
[REDACTED]	[REDACTED]
[REDACTED]	[REDACTED]

Investigators should not wait to receive additional information to fully document the event before notifying the Sponsor of a SAE. A full written summary, detailing relevant aspects of the

SAE, should follow the initial fax report. Where applicable, information from relevant hospital case records and post-mortem reports should be obtained.

Any SAE that is both unexpected and suspected to be related to treatment (SUSAR) must be reported by the Sponsor to the regulatory authorities and the REC (via the investigator) within the following time limits:

- A SUSAR that is fatal or life-threatening is to be reported to the regulatory authorities and the REC as soon as possible, and in any case no later than seven days after the Sponsor first becomes aware of it. Relevant follow-up information must be reported within an additional 8 days.
- All other SUSARs are to be reported to the regulatory authorities and the REC as soon as possible, but within a maximum of 15 days of the Sponsor first becoming aware of it.

#### **10.4.1 Reporting procedures**

The Serious Adverse Event Form must be completed as fully as possible with information relevant to the serious adverse event(s) being reported. All fields should be populated or marked accordingly if no information is available. If it is not possible to complete all sections of the Serious Adverse Event Form within 24 hours, transmission of the form must not be delayed and the outstanding information should be sent on a follow-up Serious Adverse Event Form. The investigator must complete the Serious Adverse Event Report Form as fully as possible, assess causal relationship to trial treatment and send the completed form by fax within 24 hours to the Sponsor. In cases of death reported as a serious adverse event, the report should detail the main and contributory causes of death. This information should also be accompanied by a death certificate or autopsy report, if available. The Sponsor will in any case report any death or life-threatening event to the authorities (MHRA and REC) within 7 calendar days, if it is both unexpected and considered to be drug-related, with any follow up reports within a further 8 calendar days. Any other serious adverse event that is both unexpected and considered drug-related will be reported within 15 calendar days. The original and the duplicate copies of the Serious Adverse Event Form, and the fax confirmation sheet must be kept with the case report forms at the trial site. The monitor will collect a copy of the Serious Adverse Event Form and deliver it to the Sponsor. For all serious adverse events where important or relevant information is missing, active follow-up should be undertaken. Investigators or other site personnel should inform Safety contact of any follow-up information on a previously reported serious adverse event. The follow-up information must be presented on a Serious Adverse Event Form marked as follow-up. It is necessary only to provide the new information, with the Serious Adverse Event Form signed by an investigator.

Investigators or other site personnel should send relevant or requested supporting documentation (e.g. electrocardiogram (ECG), laboratory results, autopsy report to Safety contact.)

The investigator will ensure that all the necessary information is provided within the timelines stipulated by Safety contact when the request for information is made.

Follow-up reports should be completed and transmitted following the same procedure as for the initial report. The follow-up should describe whether the event has resolved or continues, if and how it was treated, and whether the patient continued or discontinued trial participation. The form and fax confirmation sheet must be retained. The Sponsor may also request further follow-up information following review of the Serious Adverse Event Form. The investigator will make all reasonable attempts to obtain the follow-up information requested and forward it to the Sponsor as detailed above. Pregnancy follow-up should describe the outcome of the pregnancy, including any voluntary or spontaneous termination, details of the birth, and the presence or absence of any congenital abnormalities or birth defects. The investigator will provide these details via completion of a Pregnancy Follow-up form.

## 11 EVALUATION OF RESULTS

Changes in the conduct of the trial or planned analyses will be reported in the corresponding section of the trial report.

A Statistical Analysis Plan (SAP) will be developed by a qualified statistician together with a pharmacokinetic modeller. Pharmacokinetic and Statistical analysis will be performed according to this document. The SAP will specifically include details of how all: Analysis Populations, Demographic and Baseline Characteristics, Completion and Discontinuation information, Medication details, Pharmacokinetic analyses as well as Safety analyses (including oropharyngeal tolerability) and Palatability will be classified and described. The SAP will be reviewed and approved prior to analysis.

The sample size chosen for the trial is considered appropriate based on previous experience. No formal sample size calculations have been performed. In order to develop a robust population pharmacokinetic model (i.e. precisely estimated parameters), data from a minimum of 150 blood samples will be required. It is hoped that the required number of samples may be obtained from 12-18 patients. However, if problems are encountered in obtaining samples further patients may be included in the trial. In order to accommodate these problems without having to submit repeated protocol amendments the protocol states up to 18 patients for inclusion in the trial.

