## **3. TRIAL DESIGN**

### **3.1 Exit points**

The normal exit point from this trial will be when the patient completes the follow up of the second treatment period, i.e. when the patient returns to clinic for their next treatment course or for their next clinic review (it is anticipated that this will be approximately two to three weeks following 13-CRA treatment), all adverse events will be followed up to conclusion.

All patients who have at least one blood sample taken for the pharmacokinetic trial will be included in the population pharmacokinetic analysis. If the parent(s)/legal guardian or patient refuses further blood sampling the patient will be withdrawn from the trial.

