### 5. SELECTION OF PATIENTS

Up to 20 patients will be enrolled into the trial depending on the number of pharmacokinetic blood samples that are obtained from each patient. A minimum of 150 pharmacokinetic blood samples are required for adequate analysis of the patient population.

To ensure each age cohort is appropriately represented by age the trial will aim to include a minimum number of patients to the following age groups:

Age 1 - <2 years: 4 patients  
Age 2 - < 6 years: 4 patients

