## **8 PREMATURE DISCONTINUATION FROM TRIAL**

### **8.1 Early Discontinuation of an Individual Patient**

Patients and their parent(s)/legal guardian will be informed that they have the right to withdraw from the trial at any time, without prejudice to their medical care and that they are not obliged to state their reasons. In addition, the investigator may remove a patient from the trial if, in the investigator's opinion, it is not in the best interest of the patient to continue in the trial.

Any withdrawal from the trial must be fully documented in the CRF and source.

The date of discontinuation from the trial and reason (where possible) for discontinuation will be recorded on the CRF and in the patient's medical records.

- Patients may be discontinued from the trial for the following reasons:
- Withdrawal of consent
- AE
- Deviation from protocol
- Other (to be specified on the CRF by the investigator if possible)

The data recorded (including PK samples) until the time of withdrawal will be used as part of the clinical trial unless the parent(s)/legal guardian or patient requests that it is not used.

Withdrawn patients may be replaced if the overall target number of samples has not been reached (i.e. a total of 150 samples).

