### 11.3.2 Sample Size

Up to 20 patients, both male and female, aged 0 – < 21 years of age will be recruited.

There are no power calculations in this trial. The objective of this trial is to estimate the population pharmacokinetics of 13-CRA following the administration of 13-CRA liquid (test product) and extracted capsule (reference product). From a statistical point of view, the collected plasma 13-CRA concentration data are expected to relate to a non-linear, mixed effects model involving repeated measures. The developed pharmacokinetic model will estimate the parameters of the model and their associated within- and between-patient variability.

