7.1 Sample Size

Up to 20 patients, both male and female, aged 0 – < 21 years of age will be recruited.

There are no power calculations in this trial. The objective of this trial is to estimate the population pharmacokinetics of 13-CRA following the administration of 13-CRA liquid (test product) and extracted capsule (reference product). From a statistical point of view, the collected plasma 13-CRA concentration data are expected to relate to a non-linear, mixed effects model involving repeated measures. The developed pharmacokinetic model will estimate the parameters of the model and their associated within- and between-patient variability.

In order to develop a robust population pharmacokinetic model (i.e. precisely estimated parameters), data from a minimum of 150 blood samples will be required. It is hoped that the required number of samples may be obtained from 12-18 patients. However, if problems are encountered in obtaining samples further patients may be included in the trial.

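### The protocol and SAP give two entry rules for the one primary PK analysis; separately, Protocol section 11 states the patient maximum as 18 where it is 20 elsewhere

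*Protocol*

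**What the plan says.** **Who enters the PK analysis.** Protocol 3.1 states: "All patients who have at least one blood sample taken for the pharmacokinetic trial will be included in the population pharmacokinetic analysis". Section 8.3 says the same in other words. Section 8.1 adds: "The data recorded (including PK samples) until the time of withdrawal will be used as part of the clinical trial", unless the family or patient asks otherwise. Section 3.1 also withdraws a patient when the patient or family refuses further blood sampling.

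Protocol 11.3.1 defines the PK population, the basis for the primary variable, more narrowly. The patient needs at least one successful sample, must complete the trial, and must have no deviation likely to affect the PK parameters. SAP 9.1 repeats this. Section 8.3 defines completion as having finished the 14-day follow-up after Month 2 dosing. SAP sections 2 and 12 put the population PK analysis outside the SAP.

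**How many patients and samples.** Section 5 sets the target: "A minimum of 150 pharmacokinetic blood samples are required for adequate analysis of the patient population". It also gives the maximum: "Up to 20 patients will be enrolled into the trial depending on the number of pharmacokinetic blood samples that are obtained from each patient". Section 11.3.2 agrees ("Up to 20 patients, both male and female"), as do the synopsis and SAP 7.1. Protocol 11 and SAP 7.1 share an expectation: "It is hoped that the required number of samples may be obtained from 12-18 patients". Protocol 11 alone goes on to say that "the protocol states up to 18 patients for inclusion in the trial". On replacement, section 8.1 says: "Withdrawn patients may be replaced if the overall target number of samples has not been reached (i.e. a total of 150 samples".

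**The concern.** The two entry rules give opposite answers for the same patient, and section 3.1 itself creates such patients by withdrawing anyone who declines more sampling. Relative bioavailability, CL/F and V/F are the primary parameters, so the conflict concerns the data set behind the primary result. It also leaves the 150-sample requirement without a clear denominator: a total that meets 150 under the inclusive rule can fall short under the completer rule.

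The figure of 18 defeats the purpose of its own sentence. Section 11 explains it as room for further patients if sampling proves difficult, yet 18 is the top of the expected 12-18. It leaves unclear whether a 19th or 20th patient may be enrolled.

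**Working it through.** **Entry rules side by side.** Take a patient sampled on both PK days of Month 1 who then refuses further sampling.

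- Protocol 3.1: withdrawn from the trial, included in the population PK analysis.
- Protocol 8.1: samples used, unless the family or patient objects.
- Protocol 8.3: included in the PK analyses, but not a completer.
- Protocol 11.3.1 and SAP 9.1: outside the PK population.

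Protocol 11.1 says sparse sampling rules out a classical analysis, so the primary parameters come from the population model. There is one analysis with two entry rules.

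**Samples under each rule.** Sections 11 and 11.3.2 say that no sample size or power calculation was done, so there is no calculated figure to reproduce. Inputs from the documents:

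- four PK days per patient (3.2);
- five samples per PK day from age 2, where possible (4.6);
- up to three per PK day under 2 years, taken here as three (4.6);
- at least four patients under 2 (synopsis);
- target 150 (section 5).

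Assumed: exactly four under-2s, *w* withdrawals, all aged 2 or over and after Month 1, and no 24-48 hour samples. With *m* older patients:

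- completers' samples C = 4 × 12 + (m − w) × 20
- pooled samples P = C + w × 10

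12 enrolled (m = 8):
- w = 2: C = 48 + 6 × 20 = 168, no gap.
- w = 3: C = 48 + 5 × 20 = 148; P = 148 + 30 = 178.

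18 enrolled (m = 14):
- w = 8: C = 48 + 6 × 20 = 168, no gap.
- w = 9: C = 48 + 5 × 20 = 148; P = 148 + 90 = 238.

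The 12-patient result moves with the sampling rate in older patients:
- Four a day, w = 2: C = 48 + 6 × 16 = 144; P = 144 + 2 × 8 = 160.
- Eight a day, w = 5: C = 48 + 3 × 32 = 144; P = 144 + 5 × 16 = 224.
- Three a day plus every late sample (14 per completer of any age, 7 per leaver), w = 2: C = 56 + 6 × 14 = 140; P = 140 + 14 = 154.
- Three a day without late samples: even with nobody leaving, 48 + 8 × 12 = 144, so the total stays below 150 and replacement stays open.

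**Maximum of 18 or 20.** The average yield needed is 150/18 = 8.33 samples per patient at 18 and 150/20 = 7.5 at 20. The choice decides whether 150 can be reached only if the average yield is at least 7.5 but below 8.33.

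- Only the two mandatory samples on each of four PK days (8 per patient): 18 × 8 = 144, 19 × 8 = 152, 20 × 8 = 160.
- The same, but four under-2s at one a day: 16 + 14 × 8 = 128 and 16 + 16 × 8 = 144, short under both.
- The same, but four under-2s at three a day: 48 + 14 × 8 = 160 and 48 + 16 × 8 = 176, enough under both.
- Five a day in older patients, three in four under-2s: 48 + 14 × 20 = 328 and 48 + 16 × 20 = 368.

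**The case against.** Four stronger readings are tempting, and the documents do not support them.

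*The population can be chosen freely once results are seen.* Section 11 requires the SAP to be approved before analysis, 11.3.3 places analysis after populations are agreed and the database is locked, and 13.6 has evaluability decided beforehand. These safeguards stand and limit the problem. They do not remove it: the SAP leaves the population model out of scope, and in an open-label trial data may be visible before those decisions.

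*The 18 puts the 150-sample target at risk.* Section 11 reports what the protocol states rather than setting a limit. Each of the other places that give a maximum says 20, and SAP 7.1 repeats the surrounding text without the 18. The intended figure is recoverable, and the target is safe if sampling is near plan.

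*Once 150 samples are pooled, the shortfall in completers is locked in.* Section 8.1 says withdrawn patients may be replaced if the target is not reached. It does not say expressly that their samples count towards 150; that is only the natural reading, directly after the sentence that uses their data. Nor does an end to replacement end recruitment: section 5 allows enrolment to 20, and section 11 foresees further patients if sampling is difficult. In the 12-patient illustration eight places remain.

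*The shortfall is likely.* The documents give no withdrawal rate. Three leavers suffice at the bottom of the expected range; nine are needed at the top.

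One could also suppose that the model is fitted to everyone while SAP Table 14.2.3 summarises completers. Neither document says so, and 11.3.1 ties its population to the analysis of the primary variable itself.

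**Conclusion.** The conflict over non-completers is real, is in the current text, and is the main point: one primary analysis, two entry rules, and no document that settles which applies. It should be resolved before analysis. Its numerical effect is conditional. Under the assumptions shown, the completers' total falls to 148 while the pooled total is 178 (12 enrolled, three leaving) or 238 (18 enrolled, nine leaving). These are illustrations, not forecasts.

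The 18 is an error of statement with little practical effect. It bears on the 150 only at an average yield from 7.5 to just under 8.33 samples per patient.

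Two minor inconsistencies also need reconciling: the four-patient minimum is for 0 to under 2 years in the synopsis but 1 to under 2 in section 5, and samples per PK day are a minimum of five in 4.6 but a maximum of five in Appendix I.

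**What to change.** 1. Before analysis, remove the completion requirement from Protocol 11.3.1 and SAP 9.1. Every patient with at least one evaluable sample then enters, subject to the existing exclusion for deviations likely to affect the PK parameters. This agrees with 3.1, 8.1 and 8.3, and with 11.1, which says individual parameters can be obtained from as little as one sample. If the sponsor prefers the completer rule, amend 3.1, 8.1 and 8.3 to match. Either way, state that the rule governs the population model.
2. In 8.1, state that the 150 counts only samples entering that analysis.
3. In section 11, change the maximum from 18 to 20.
4. Reconcile the age band (synopsis, section 5) and the samples per PK day (4.6, Appendix I).

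A rule for replacing patients not sampled on both formulations would be optional, since section 5 already leaves room up to 20.

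The cost is wording only. SAP 16 describes the patients' ages in the past tense, which suggests enrolment was already known. If it has closed, the maximum and the replacement rule become clarifications for the report, and item 1 is the part still needed before analysis.

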### 11.1 Pharmacokinetic analysis

Since a sparse sampling approach is to be employed in the present trial it is not possible to use a classical analysis to obtain PK parameter estimates. Therefore, a population-PK approach will be applied. In the population approach all data from different individuals are fitted simultaneously using a non-linear, mixed effects modelling approach and post hoc individual kinetic parameters can be calculated with as few samples as one per individual.

Data will be analysed using the mixed effects non-linear regression modelling programme, NONMEM (version V II; ICON). Post processing of NONMEM output will be undertaken with an appropriate statistical package such as R (current version).

Preliminary analyses will focus on the structural and variance models. One and two compartment models with first and zero order inputs will be implemented. Between patient variability will be assumed to be log-normally distributed, and residual error will be modelled using additive, proportional and combined error structures.

Biologically plausible covariates will be included in the model for analysis e.g. age, weight. A multivariate analysis will be performed, details of this analysis will be included in the SAP. Several criteria can be used to evaluate the improvement in the model performance and thus select the final model. Comparisons of hierarchical models are based on the objective function value, i.e. two times the negative log likelihood value. Changes in the objective function value  $> 7.88$  ( $p < 0.005$ ) are accepted as statistically significant. The other selection criteria used include improvement in the goodness of fit and residual plots, increased precision in parameter estimation, and reduced variance of between patient and residual errors. An assessment of model appropriateness will be undertaken using visual predictive checks and posterior predictive checks. This will be based on the final covariate model.

The metabolite 4-oxo-13-cis-retanoic acid will also be evaluated. The absorption function,  $CL/F$ ,  $V/F$  will be considered as primary PK parameters; secondary PK parameters (such as  $T_{max}$ ,  $C_{max}$ , AUC and half-life) will be calculated from the primary model parameters. .

